4.3 Sample Size

GPP is designated as the specified rare and intractable disease in Japan and patient number is quite limited. Assuming the Clinical Response rate of adalimumab in GPP is similar to PASI 75 response in plaque psoriasis, 50% to 60% as expected response rate in adalimumab treatment and 10% as a threshold response rate is hypothesized.

A sample size of 6 to 10 provides over 90% power to detect the difference between expected Clinical Response rate (50 to 60%) and threshold response rate (with no medication, 10%) in GPP, using a one sample Chi-square test with 2.5% one-sided significance level. In case of using Fisher's exact test, an exact binomial test with a nominal 0.025 one-sided significance level will have 82% power to detect the difference between the threshold proportion of 10% and the expected proportion of 50%.

Therefore, the target number of subjects is set 10 subjects, taking the study feasibility into consideration.

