6.5 Definition of Missing Data Imputation

The following methods will be used to impute missing values in the efficacy analyses. In general, missing Baseline and safety data will not be imputed. In addition, an observed case analysis will be performed.

Baseline Value is Missing

Subjects will be excluded from analysis of change from baseline if baseline evaluation is missing.

Non-Responder Imputation (NRI)

The NRI approach is used for binary efficacy variables. These variables can take values of 'Achieved' or 'Not Achieved' or may be missing for any reason including discontinuation from study. According to the NRI imputation approach, all missing value will be considered as 'Not Achieved.'

Last Observation Carried Forward (LOCF)

For continuous variables, the following rules will be used for the LOCF approach:

1. Baseline and pre-baseline values will not be used to impute the missing post-baseline values.
2. Missing values after Study Day 1 will be imputed using the latest non-missing values after Day 1 and prior to the missing value. If there are no non-missing values after baseline, then the LOCF value will be missing.

Observed Cases (OC)

Observed case analysis will be performed such that missing values will not be imputed.

Imputation of Missing Dates

For baseline, efficacy, and safety parameters, if the day and/or month are missing, the following conventions will be used to impute the missing dates:

- 01 for missing start day
- End of month for missing end day

- January 1st for missing start month
- December 31st for missing end month

In case of missing or partially missing dosing dates, the dates will not be imputed.

In case of missing or partially missing adverse event start and stop dates, the dates will be imputed by comparing to the first dosing date so that the corresponding adverse events will be made treatment-emergent, whenever possible.

Rounding

Rounding will be performed only for presentation of results. No rounding will be performed before or during computations. The ROUND function of SAS will be used to round results for presentation.

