9.1 Study Drug Exposure

The duration (days) of exposure to study drug will be summarized using the number of subjects treated, mean, standard deviation, minimum, median, and maximum. Duration of exposure is defined the number of days since first dose of study drug through the last dose date plus 14 days. For interim analysis at Week 24, the Week 24 dosing date will be used instead of last dose plus 14 days only for ongoing subjects. In addition, the number and percentage of subjects exposed to study drug will be summarized for the following duration intervals.

1 – 15 days
16 – 29 days
30 – 57 days
58 – 85 days
86 – 113 days
114 – 141 days
142 – 169 days
170 – 197 days
198 – 225 days
226 – 253 days
254 – 281 days
282 – 309 days
310 – 337 days
338 – 365 days
> 365 days

Exposure to study drug (total patient years) will be summarized.

Cumulative Dose (mg)

Cumulative dose is derived as dose per administration times the number of injections given during the study. Cumulative dose will be summarized using the number of subjects treated, mean, standard deviation, minimum, median, and maximum.

The Number of Study Drug Injections

The number of injections received at each scheduled time point by subject will be summarized with numbers.

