9.3 Study Drug Dose

80 mg starting at Baseline (Week 0) and 40 mg eow on and after Week 2 until Week 50. Dose escalation to 80 mg eow is allowed for subjects who do not have appropriate response and meeting dose escalation criteria on or after Week 8. Dose reduction is not allowed after dose escalation until the study end. Treatment of study drug will not occur at Week 52.

The number of adalimumab injections received by subjects will be summarized.

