11.2 Analysis of Adverse Events

11.2.1 Treatment-Emergent Adverse Events

Treatment-emergent adverse events (TEAEs) are defined as events that begin or worsen either on or after the first dose day of the study medication and within 70 days after the last dose of the study medication. Treatment-emergent AEs will be summarized separately for the first half period (Week 0 to Week 24), the second half period (Week 24 to Week 52), and entire period (Week 0 to Week 52).

For the interim analysis at Week 24, treatment-emergent adverse events are defined as any event with an onset or worsening on or after the first dose of study drug and on or prior to the Week 24 dosing date for subjects who continued in the study after Week 24, and up to 70 days after the last dose of study drug for subjects who discontinued prior to Week 24 visit.

Treatment-emergent adverse events will be summarized and presented using primary Medical Dictionary for Regulatory Activities (MedDRA) system organ classes (SOCs) and preferred terms (PTs) according to the version of the MedDRA coding dictionary used for the study at the time of database lock. The actual version of the MedDRA coding dictionary used will be noted in the clinical study report. The system organ classes will be presented in alphabetical order and the preferred terms will be presented in alphabetical order within each system organ class.

For the Dose Escalation set, TEAEs will be reported before the date of dose escalation and also on or after the date of dose escalation, separately.

Adverse Event Overview

The number and percentage of subjects experiencing treatment-emergent adverse events will be summarized for the following adverse event categories.

- Any treatment-emergent adverse event

- Any treatment-emergent adverse event that was rated as possibly related to study drug by the investigator (Reasonable Possibility)
- Any treatment-emergent severe adverse event
- Any treatment-emergent serious adverse event
- Any treatment-emergent adverse event leading to discontinuation of study drug
- Any treatment-emergent serious adverse event that was rated as possibly related to study drug by the investigator (Reasonable Possibility)
- Any treatment-emergent adverse event leading to death
- Any treatment-emergent adverse event of special interest
- Any Deaths

Adverse Events by SOC and PT

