Adverse events will also be summarized by maximum relationship to study, as assessed by the investigator. If a subject has an adverse event with unknown relationship, then the subject will be counted in the relationship category of "unknown," even if the subject has another occurrence of the same adverse event with a relationship present. The only exception is if the subject has another occurrence of the same adverse event with a relationship assessment of "Reasonable Possibility." In this case, the subject will be counted under the "Reasonable Possibility" category, respectively.

Adverse Event Rates per 100 Patient Years of Study Drug Exposure

Incidence rates per 100 patient years of exposure to study drug will be presented for adverse event overviews and for adverse events by SOC and PT.

The treatment-emergent adverse event rate per 100 patient years of exposure will be calculated overall, for each primary SOC, and each PT. For this calculation, 1 year will be considered to be 365.25 days. The numerator of the overall rate, the SOC rate, or the PT rate, will be the total number of treatment-emergent adverse events reported overall,

for the SOC, or for the PT, respectively; i.e., a subject can be counted more than once overall, for a SOC, and for a PT. The denominator of the rates will be the total number of days exposed to study drug summed across all treated subjects divided by 365.25, and rounded to one decimal place. The adverse event rate per 100 subject-years of exposure will be calculated as [(numerator/denominator)]*100. The number of adverse events reported (numerator), the total number of years of study drug exposure (denominator), and the adverse event rate per 100 subject-years will be presented overall, for each SOC, and for each PT.

Adverse Events of Special Interest (AESI)

The analysis of treatment-emergent adverse events of special interest based on Standardized MedDRA Queries (SMQs) or Company MedDRA Queries (CMQs) will be presented for the adverse event overviews and for adverse events by SOC and PT.

The final analyses will follow the latest version of Product Safety Statistical Analysis Plan (PSSAP).

The current list of AEs of special interest in PSSAP (version 5.0, dated 20Jan2016) for treatment with adalimumab is:

- Any Infections AE
- Any Serious Infection AE
- Any Legionella Infection AE
- Any Diverticulitis AE
- Any Opportunistic Infection AE (Excluding Oral Candidiasis and TB)
- Any Oral Candidiasis AE

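### The adverse event rate per 100 patient-years counts events to 70 days after the last dose but exposure only to 14 days after it, so it may be overstated by 0% to about 15% in completers

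*SAP*

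**What the plan says.** The rate is defined in SAP 11.2.1, in the paragraph on rates per 100 patient-years. The numerator "will be the total number of treatment-emergent adverse events reported overall", or the corresponding total for a system organ class or preferred term, and a subject may contribute several events. The same section counts an event as treatment-emergent if it begins or worsens from the first dose day and "within 70 days after the last dose of the study medication".

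The denominator is the sum of days exposed to study drug over all treated subjects, "divided by 365.25, and rounded to one decimal place". The only definition of exposure duration is in SAP 9.1: the days since the "first dose of study drug through the last dose date plus 14 days".

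For the Week 24 interim the SAP makes a special provision. For subjects still in the study, SAP 11.2.1 stops events at the Week 24 dosing date and SAP 9.1 stops exposure at that same date. For subjects who discontinued before Week 24, the 70-day and 14-day limits still apply.

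On rounding, SAP 6.5 states: "No rounding will be performed before or during computations".

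**The concern.** An exposure-adjusted rate is interpretable when events and person-time are collected over the same interval. Here the event interval runs 56 days longer per subject (70 − 14 = 56). Any event with onset in those days enters the numerator, while the days themselves are left out of the denominator. Followed as written, this can push the rate in one direction only, upwards.

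The late interval is not empty by design. Protocol 6.1.4 collects adverse events until 70 days after study drug is stopped. It also requires serious events and events of special interest reported at the 70-day call to be entered in the clinical database.

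The rates are a stated safety output, planned for the overview (including events of special interest) and by system organ class and preferred term. The primary endpoint is not affected, nor are the counts and listings of treatment-emergent events.

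The rounding clause is a separate and smaller matter. It contradicts SAP 6.5, and its size is checked below.

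**Working it through.** The documents state no adverse event rate or patient-year total, so there is no planned figure to reproduce. The check is direct arithmetic.

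**Inputs**
- Subjects: "the target number of subjects is set 10 subjects" (SAP 4.3).
- Last scheduled dose: Week 50, from "40 mg eow on and after Week 2 until Week 50" (SAP 9.3). With the first dose on Day 1, this is Day 7 × 50 + 1 = 351.
- Exposure ends at last dose + 14 days (SAP 9.1). The event window ends at last dose + 70 days (SAP 11.2.1).
- Assumption: r is the event rate after last dose + 14 days, relative to the rate during exposure. The documents give no value. I take 0 to 1.

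**Completers, final analysis**
- Exposure: 351 + 14 = 365 days.
- Event window: 351 + 70 = 421 days.
- Overstatement relative to the rate during exposure = 56r / 365:

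| r | Overstatement |
|---|---|
| 0 | 0% |
| 0.25 | 3.8% |
| 0.5 | 7.7% |
| 0.75 | 11.5% |
| 1 | 15.3% (421/365 = 1.153) |

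Counting exposure as 364 days instead of 365 gives 420/364 = 1.154, so the convention does not matter.

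**Pooled rate with early discontinuers (r = 1, ten subjects)**
- One stops with last dose at Week 8 (exposure 71 days, event window 127 days): (9 × 421 + 127) / (9 × 365 + 71) = 3916/3356 = 1.167.
- Two stop with last dose at Week 8: (8 × 421 + 2 × 127) / (8 × 365 + 2 × 71) = 3622/3062 = 1.183.
- One stops with last dose at Week 2 (29 and 85 days): (9 × 421 + 85) / (9 × 365 + 29) = 3874/3314 = 1.169.

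**Week 24 interim**
- Ongoing subjects: events and exposure both end at the Week 24 dosing date (Day 169). The ratio is 1.
- If one of ten stopped with last dose at Week 8 (r = 1): (9 × 169 + 127) / (9 × 169 + 71) = 1648/1592 = 1.035.

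**Illustration with an assumed 50 treatment-emergent events in ten completers**
- SAP denominator: 3650/365.25 = 9.993, rounded to 10.0. Rate 500.0 per 100 patient-years.
- Rounding removed: 50/9.993 × 100 = 500.3.
- Person-time matched to the 70-day window: 4210/365.25 = 11.53 patient-years. Rate 433.8.

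Against this last definition the numerators are identical, so the ratio is 421/365 whatever r is. The 0% to 15% range applies to the comparison with events restricted to the exposure window.

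**Rounding alone**
- Largest error = 0.05 / patient-years: 0.05/10 = 0.5% at the final analysis, 0.05/4.6 = 1.1% at the interim.
- Ten completers: 9.993 becomes 10.0, a change of −0.07%.
- Ten ongoing subjects at the interim: 10 × 169/365.25 = 4.627 becomes 4.6, a change of +0.6%.
- The sign depends on the total.

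**The case against.** The strongest counter-argument is that SAP 11.2.1 labels the entire summary period as Week 0 to Week 52. A completer's exposure ends on Day 365, which is the nominal Week 52 day in the SAP 6.4 visit windows. If the label is meant to cut events there, numerator and denominator nearly coincide for completers and the 15% disappears. This stands as a possible reading. However, the rate paragraph states no such cut; it uses total treatment-emergent events, and those are defined to 70 days. Under the label reading, subjects who stop early would still be mismatched.

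Second, 15% requires events to continue, and to be captured, at the same rate as during exposure. After the final visit, follow-up is one phone call, and the explicit database requirement for that call in Protocol 6.1.4 names only serious events and events of special interest. Capture of other late events may be lower. This stands too, and is why a range is given.

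Third, the study has no comparator, no comparison of these rates is planned, and the table prints events, patient-years and rate side by side. That limits the consequence but does not align the windows.

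Three stronger readings are tempting and not supported:
- A reader might infer that the rounding clause biases the rates. It does not: the effect is small and goes either way, and because the rounded denominator is the one printed, the rate can be reproduced from the table.
- A reader might infer a several-fold distortion from a subject who stops after the Week 2 dose (85/29 = 2.93). That is a ratio for one subject. The SAP rate is pooled, and with one such subject in ten the factor is 1.169.
- A reader might infer that rounding becomes serious in the small Dose Escalation set. The SAP reports events before and after escalation for that set but specifies no rate and no split of exposure for it.

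**Conclusion.** The point holds as a mismatch of windows in a stated safety output. As written, the final rate can be overstated and cannot be understated. The size for completers is 0% to about 15% (7.7% if the late event rate is half the rate during exposure). Pooled over ten subjects with one or two early discontinuers, the figure at equal rates is about 17% to 18%. At the Week 24 interim only early discontinuers contribute.

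These figures assume ten subjects, a last dose at Week 50 for completers, follow-up to 70 days, and a late event rate no higher than the rate during exposure. The documents do not give that rate, so the actual overstatement cannot be fixed in advance. If the Week 0 to Week 52 label is intended as a cut-off, the problem narrows to early discontinuers, but the SAP would need to say so.

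The rounding clause is a genuine contradiction of SAP 6.5 with a negligible effect. Overall this is a minor correction.

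**What to change.** In SAP 11.2.1, use one window for both parts of the rate and name it in the table title. Either option works:
- events with onset through last dose + 14 days, over exposure time as SAP 9.1 defines it; or
- all treatment-emergent events, over person-time from first dose to the earlier of last dose + 70 days and last contact.

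State whether the Week 0 to Week 52 label cuts events for the rate. The full 70-day counts and listings of treatment-emergent events stay unchanged, so no safety information is lost. The interim rule for ongoing subjects is already aligned and needs no change.

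For consistency, remove the one-decimal rounding from the computation of the denominator and round for display only, as SAP 6.5 requires.

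The cost is a small edit to the SAP text and one extra derivation. The downside is that reported rates will be slightly lower than under the current text.

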11.2.2 Listing of Adverse Events

The following additional summaries of adverse events will be prepared.

- Listing of treatment-emergent adverse events
- Listing of subject numbers associated with each PT for treatment-emergent adverse events
- Listing of treatment-emergent serious adverse events
- Listing of pre-treatment serious adverse events
- Listing of treatment-emergent adverse events that led to discontinuation of study drug
- Listing of treatment-emergent fatal adverse events.
- Listing of deaths
- Listing of treatment-emergent adverse events of special interest

11.3 Analysis of Laboratory Data

Laboratory test variables are specified in Table 7. Laboratory test variables will use standard units.

Table 7. Clinical Laboratory Tests

Hematology	Clinical Chemistry	Urinalysis ^a
Hematocrit	Blood Urea Nitrogen (BUN)	Specific gravity
Hemoglobin	Creatinine	Ketones
Red Blood Cell count	Total bilirubin	pH
White Blood Cell count	Serum glutamic-pyruvic transaminase/alanine transaminase (SGPT/ALT)	Protein
Neutrophils (Stab, Seg)	Serum glutamic-oxaloacetic transaminase/aspartate transaminase (SGOT/AST)	Blood
Bands (Stab)	Alkaline phosphatase	Glucose
Lymphocytes	Sodium	
Monocytes	Potassium	
Basophils	Calcium	
Eosinophils	Inorganic phosphorus	
Platelet count (estimate not acceptable)	Uric acid	
	Cholesterol	
	Total protein	
	Glucose	
	Triglycerides	
	Albumin	
	hs-CRP	
Additional Blood Samples Collected		
β -hCG (serum pregnancy test) QuantiFERON-TB Gold or T-SPOT TB (IGRA) HIV HBV HCV ANA anti-dsDNA – if ANA positive Pharmacokinetic, Anti-adalimumab antibody		

a. A microscopic analysis will be performed by the central laboratory, in the event the dipstick results show protein, ketones or blood greater than negative or glucose greater than normal.

11.3.1 Variables and Criteria Defining Abnormality

The liver specific laboratory tests include the serum glutamic-pyruvic transaminase (SGPT/ALT), serum glutamic-oxaloacetic transaminase (SGOT/AST), alkaline

phosphatase and total bilirubin. Each of these laboratory values will be categorized as follows:

1. $< 1.5 \times \text{ULN}$,
2. $\geq 1.5 \times \text{ULN} \text{ TO } < 3 \times \text{ULN}$,
3. $\geq 3 \times \text{ULN} \text{ TO } < 5 \times \text{ULN}$,
4. $\geq 5 \times \text{ULN} \text{ TO } < 8 \times \text{ULN}$, and
5. $\geq 8 \times \text{ULN}$,

where ULN is the upper normal limit.

Shift tables showing shift from Baseline to maximum and final values will be presented using these five categories.

A listing of potentially clinically significant liver function laboratory values will be provided. The listing will include all subjects who met any of the following 4 criteria:

1. $\text{ALT} \geq 2.5 \times \text{ULN}$, or
2. $\text{AST} \geq 2.5 \times \text{ULN}$, or
3. Alkaline Phosphatase $\geq 2.5 \times \text{ULN}$, or
4. Total Bilirubin $\geq 1.5 \times \text{ULN}$.

For selected laboratory parameters (Hematology: Hemoglobin, Platelet count, WBC, Neutrophils, Lymphocytes; Clinical Chemistry: ALT, AST, Alkaline Phosphatase, γ -GTP, Total Bilirubin, Albumin, CPK, Creatinine, Uric Acid, Calcium, Sodium, Potassium, Inorganic Phosphorus, Magnesium, Glucose, Cholesterol, Triglycerides) with Common Toxicity Criteria (CTC), Potentially Clinically Significant (PCS) Laboratory Findings (Common Toxicity Criteria CTC [Version 4.0] Grades 3 and 4) will be assessed.

The following table describes the Criteria for Potentially Clinically Significant Laboratory Findings:

Table 8. Potentially Clinically Significant Laboratory Findings

Laboratory Parameter	CTC Grade 1	CTC Grade 2	CTC Grade 3	CTC Grade 4
Hemoglobin – Low (G/L)	< LLN – 100	< 100 – 80	< 80	–
Hemoglobin – High (G/L)	CH > 0.0 – 20	CH > 20 – 40	CH > 40	–
Platelet count ($\times 10^9/L$)	< LLN – 75	< 75 – 50	< 50 – 25	< 25
WBC ($\times 10^9/L$)	< LLN – 3.0	< 3.0 – 2.0	< 2.0 – 1.0	< 1.0
Neutrophils ($\times 10^9/L$)	< LLN – 1.5	< 1.5 – 1.0	< 1.0 – 0.5	< 0.5
Lymphocytes ($\times 10^9/L$)	< LLN – 0.8	< 0.8 – 0.5	< 0.5 – 0.2	< 0.2
ALT	> ULN – 3.0 \times ULN	> 3.0 – 5.0 \times ULN	> 5.0 – 20.0 \times ULN	> 20.0 \times ULN
AST	> ULN – 3.0 \times ULN	> 3.0 – 5.0 \times ULN	> 5.0 – 20.0 \times ULN	> 20.0 \times ULN
Alkaline phosphatase	> ULN – 2.5 \times ULN	> 2.5 – 5.0 \times ULN	> 5.0 – 20.0 \times ULN	> 20.0 \times ULN
γ -GTP	> ULN – 2.5 \times ULN	> 2.5 – 5.0 \times ULN	> 5.0 – 20.0 \times ULN	> 20.0 \times ULN
Total bilirubin	> ULN – 1.5 \times ULN	> 1.5 – 3.0 \times ULN	> 3.0 – 10.0 \times ULN	> 10.0 \times ULN
Albumin (G/L)	< LLN – 30	< 30 – 20	< 20	–
CPK	> ULN – 2.5 \times ULN	> 2.5 \times ULN – 5.0 \times ULN	> 5.0 \times ULN – 10.0 \times ULN	> 10.0 \times ULN
Creatinine*	> ULN – 1.5 \times ULN; or > 1 – 1.5 \times BL	> 1.5 – 3.0 \times ULN or > 1.5 – 3.0 \times BL	> 3.0 – 6.0 \times ULN or > 3.0 \times BL	> 6.0 \times ULN
Uric Acid (MCMOL/L)	> ULN – 590	–	–	> 590
Calcium – Low (MMOL/L)	< LLN – 2.0	< 2.0 – 1.75	< 1.75 – 1.5	< 1.5
Calcium – High (MMOL/L)	> ULN – 2.9	> 2.9 – 3.1	> 3.1 – 3.4	> 3.4
Sodium – Low (MMOL/L)	< LLN – 130	–	< 130 – 120	< 120

Table 8. Potentially Clinically Significant Laboratory Findings (Continued)

Laboratory Parameter	CTC Grade 1	CTC Grade 2	CTC Grade 3	CTC Grade 4
Sodium – High (MMOL/L)	>ULN – 150	> 150 – 155	> 155 – 160	> 160
Potassium – Low (MMOL/L)	< LLN – 3.0	–	< 3.0 – 2.5	< 2.5
Potassium – High (MMOL/L)	> ULN – 5.5	> 5.5 – 6.0	> 6.0 – 7.0	> 7.0
Inorganic Phosphorus (MMOL/L)	< LLN – 0.8	< 0.8 – 0.6	< 0.6 – 0.3	< 0.3
Magnesium - Low (MMOL/L)	< LLN – 0.5	< 0.5 – 0.4	< 0.4 – 0.3	< 0.3
Magnesium - High (MMOL/L)	> ULN – 1.23	–	> 1.23 – 3.30	> 3.30
Glucose – Low (MMOL/L)	< LLN – 3.0	< 3.0 – 2.2	< 2.2 – 1.7	< 1.7
Glucose – High (MMOL/L)	> ULN – 8.9	> 8.9 – 13.9	> 13.9 – 27.8	> 27.8
Cholesterol (MMOL/L)	> ULN – 7.75	> 7.75 – 10.34	> 10.34 – 12.92	> 12.92
Triglycerides (MMOL/L)	1.71 – 3.42	> 3.42 – 5.7	> 5.7 – 11.4	> 11.4

CH = change in ULN or change in baseline, if baseline > ULN; ULN = upper limit of normal range; LLN = lower limit of normal range; BL = baseline;

* = identify by ULN if baseline is normal else use BL if baseline is abnormal;

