3.0 Introduction

Generalized Pustular Psoriasis (GPP) is severe form of psoriasis and inflammatory disease of undetermined cause, which is characterized by generalized cutaneous erythema along with acute pyrexia as well as multiple sterile pustules. This disease has a very low incidence in Japan, and the effective treatments are limited. Therefore, it is designated as a specified rare and intractable disease by the Ministry of Health, Labour and Welfare (MHLW).

GPP may either be preceded by plaque psoriasis, or arise without a prior history of plaque psoriasis, classically after withdrawal of systemic glucocorticosteroids,¹ and recently the studies for disease pathogenesis have been identified specific gene region susceptible to GPP.² GPP is characterized by pyrexia with chills and extensive skin erythema, where tender pustules form and then coalesce into lakes of pus. Desquamation from the pustules occurs thereafter, which is accompanied by nail plate changes (thickening and onycholysis), complaint of general malaise, and with a high frequency, mucosal symptoms, arthritis, and eye symptoms. These symptoms significantly impair quality of life (QOL) and markedly affect daily living. GPP is also characterized by multiple recurrences, and rarely, patients experience capillary leak syndrome, respiratory failure, or secondary amyloidosis, and are also at risk for death from cardiac or circulatory failure, general debility, and infections.

In the acute phase of the disease, GPP requires intense management of the general condition. Once the symptoms are relatively stable, management of skin symptom is important. In Japan, some systemic treatments are approved: etretinate, cyclosporine, and infliximab. All these treatments are demonstrated to be effective for GPP, and improve skin symptom and patient QOL. However, etretinate is teratogenic and causes liver disorder, while cyclosporine sometimes causes renal disorder and hypertension. For these reasons, their use cannot be continued for long-term disease management in some patients from the safety point of view. Infliximab, which contains murine protein, may rarely cause anaphylactic symptoms. Loss of response (secondary failure patients) has

been also observed during treatment for the long-term use, and actions to be taken for such reduced response are clinically significant. These limitations of current treatments highlight the need for new therapeutic options for GPP.

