15. Prior exposure to medications that have a potential or known association with progressive multifocal leukoencephalopathy (PML) (i.e., natalizumab [Tysabri®], rituximab [Rituxan®], efalizumab [Raptiva®]).
16. Subject with any active viral infection that makes the subject an unsuitable candidate for the study based on the investigator's clinical assessment.
17. Hepatitis B: HBs Ag positive (+) or detected sensitivity on the HBV-DNA PCR qualitative test for HBc Ab/HBs Ab positive subjects.
18. Subject with known hypersensitivity to the excipients of adalimumab.
19. Positive pregnancy test at the Screening (serum) or the Baseline (urine).
20. Female who is breast-feeding or considering becoming pregnant during the study.
21. History of clinically significant drug or alcohol abuse in the last 12 months.
22. History of demyelinating disease (including myelitis) or neurologic symptoms suggestive of demyelinating disease.
23. History of moderate to severe congestive heart failure (NYHA class III or IV), recent cerebrovascular accident and/or any other condition which, in the opinion of the investigator, would put the subject at risk by participation in the study.

24. Current evidence of dysplasia or history of malignancy (including lymphoma and leukemia) other than a successfully treated non-metastatic cutaneous squamous cell carcinoma, basal cell carcinoma or localized carcinoma in situ of the cervix.
25. Chronic recurring infections or active TB.
26. Infection(s) requiring treatment with intravenous (IV) anti-infectives (antibiotics, antivirals, antifungals) within 30 days prior to Baseline or oral anti-infectives (antibiotics, antivirals, antifungals) within 14 days prior to Baseline.
27. History of invasive infection (e.g., listeriosis, histoplasmosis), human immunodeficiency virus (HIV).
28. Screening laboratory and other analysis show any of the following abnormal results:
 - AST, ALT $> 1.75 \times$ upper limit of the reference range;
 - WBC count $< 3.0 \times 10^9/L$;
 - Electrocardiogram (ECG) – with clinically significant abnormalities;
 - Total bilirubin ≥ 3 mg/dL; except for subjects with isolated elevation of indirect bilirubin relating to Gilbert syndrome;
 - Serum creatinine > 1.6 mg/dL.
29. Subject is considered by the Investigator, for any reason, to be an unsuitable candidate for the study.

Rationale for the Exclusion Criteria

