11.3.2 Statistical Methods

Mean changes from baseline to each post-baseline visits (as defined in Table 1) and final value in continuous laboratory parameters will be summarized with the baseline mean, visit mean, change from baseline mean, standard deviation, minimum value, median, and maximum value.

Laboratory data values will be categorized as low, normal, or high based on normal ranges of the laboratory used in this study. Cross (shift) tables from baseline to the minimum/maximum/final values according to the normal range will be provided for each hematology, clinical chemistry parameter and urinalysis parameters. The shift tables will cross tabulate the frequency and percentage of subjects with baseline values below/within/above the normal range versus minimum/maximum/final values below/within/above the normal range.

Incidence of abnormal laboratory values for hematology, clinical chemistry parameter and urinalysis parameters will be provided.

Scatter plot of Baseline values versus the final values in laboratory parameters will be provided.

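### For creatinine baselines within or above the normal range, the SAP Table 8 footnote selects the less sensitive Grade 3 limit, so a more than threefold rise from a normal baseline is not flagged as PCS unless it exceeds 3 × ULN

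*SAP*

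**What the plan says.** SAP 11.3.1 says that for 22 selected analytes "Potentially Clinically Significant (PCS) Laboratory Findings (Common Toxicity Criteria CTC [Version 4.0] Grades 3 and 4) will be assessed". Table 8 gives the limits. For creatinine, Grade 3 is "> 3.0 – 6.0 \times ULN or > 3.0 \times BL". Grade 4 is above 6.0 × ULN, with no baseline limit. An asterisk on the creatinine row leads to this rule: "identify by ULN if baseline is normal else use BL if baseline is abnormal".

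The SAP's classification of laboratory values elsewhere has three classes. SAP 11.3.2 states: "Laboratory data values will be categorized as low, normal, or high based on normal ranges of the laboratory used in this study". The footnote does not say whether 'abnormal' means high only, or low as well.

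The chemistry analytes listed for PCS assessment end with "Total Bilirubin, Albumin, CPK, Creatinine, Uric Acid, Calcium, Sodium, Potassium, Inorganic Phosphorus, Magnesium, Glucose, Cholesterol, Triglycerides", and gamma-GTP comes just before that run. SAP 11.3 says "Laboratory test variables are specified in Table 7". Neither that table nor protocol Table 2 contains gamma-GTP, CPK or magnesium.

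**The concern.** Read alone, the Table 8 cell catches two kinds of creatinine abnormality: a high absolute value and a large rise from the subject's own baseline. The footnote leaves one criterion per subject. For a subject who starts in the normal range the surviving criterion is the absolute one, so the baseline limit is switched off for the subjects in whom it would detect a large rise early. For a subject who starts above the range the surviving criterion is the relative one, so a value above 3 × ULN need not be flagged.

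This bears on the safety report rather than on efficacy. The protocol names a renal risk for a drug that some subjects may still be tapering until Week 8: "cyclosporine sometimes causes renal disorder and hypertension" (protocol 3.0; taper in 5.1 and 5.2.3.2). With ten subjects, one missing flag turns a PCS count of 1/10 into 0/10. The SAP gives the liver tests five ULN bands and a separate listing; creatinine has neither, so the PCS grade is its only tabulated severity category.

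**Working it through.** The plan states no figure on this point, so there is none to reproduce. The check compares the limit that the footnote selects with the one it drops.

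**Inputs.** The Grade 3 limits and the footnote come from SAP Table 8, the PCS rule (Grades 3 and 4) from SAP 11.3.1, and the screening cap, "Serum creatinine > 1.6 mg/dL", from protocol 5.2.2. The documents give neither ULN nor LLN for creatinine, so the main results are in units of ULN. Let BL be the baseline value.

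**Rule as written.**
- Normal baseline (LLN ≤ BL ≤ ULN): applied limit 3 × ULN, dropped limit 3 × BL. Since BL ≤ ULN, the applied limit is the higher one, or equal at BL = ULN.
- High baseline (BL > ULN): applied limit 3 × BL, dropped limit 3 × ULN. The applied limit is again the higher one.
- Low baseline (BL < LLN), if 'abnormal' includes low: applied limit 3 × BL, dropped limit 3 × ULN. Here the applied limit is the lower, more sensitive one.

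Fold rise needed for a flag = applied limit / BL. The classes below assume, for illustration, LLN = 0.5 × ULN.

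| BL (× ULN) | Class | Applied limit (× ULN) | Dropped limit (× ULN) | Rise needed for a flag |
|---|---|---|---|---|
| 0.4 | low | 1.2 | 3.0 | > 3.0-fold |
| 0.5 | normal | 3.0 | 1.5 | > 6.0-fold |
| 0.6 | normal | 3.0 | 1.8 | > 5.0-fold |
| 0.8 | normal | 3.0 | 2.4 | > 3.75-fold |
| 0.9 | normal | 3.0 | 2.7 | > 3.33-fold |
| 1.0 | normal | 3.0 | 3.0 | > 3.0-fold |
| 1.25 | high | 3.75 | 3.0 | > 3.0-fold |

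In the last row, a value between 3.0 and 3.75 × ULN (a 2.4- to 3.0-fold rise, since 3.0 / 1.25 = 2.4) is above the ULN limit but is not flagged.

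**In mg/dL, under assumptions.** Take ULN between 0.8 and 1.3 mg/dL and a baseline of 0.6 mg/dL that lies within the normal range. The footnote's limit is 3 × 0.8 = 2.4 to 3 × 1.3 = 3.9 mg/dL, a 4.0- to 6.5-fold rise. The baseline limit would be 3 × 0.6 = 1.8 mg/dL. If 0.6 were below LLN and low counted as abnormal, 1.8 would apply.

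**Grade 4.** Taken literally, a subject graded by baseline cannot reach Grade 4, because that cell has no baseline limit. The effect on PCS status is small: if BL ≤ 2 × ULN, any value above 6 × ULN already exceeds 3 × BL and is flagged at Grade 3. A screening value above 2 × ULN under the 1.6 mg/dL cap would require ULN below 1.6 / 2 = 0.8 mg/dL.

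**If both limits counted.** Grade 3 would start above 3 × min(BL, ULN): 1.5, 1.8, 2.4 and 2.7 × ULN for baselines of 0.5, 0.6, 0.8 and 0.9 × ULN. Every rise of more than threefold from a normal baseline would then be flagged.

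**Panel check.** SAP 11.3.1 lists 5 hematology and 17 chemistry analytes, 22 in all. Exactly three are missing from SAP Table 7 and protocol Table 2: gamma-GTP, CPK and magnesium.

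**The case against.** The strongest reply is that the footnote is a prespecified choice that tells the programmer which limit applies, and that nothing is hidden. SAP 11.3.2 provides change from baseline with minimum and maximum, shift tables from baseline to the maximum value, incidence of abnormal values and scatter plots. Protocol 8.1.5 adds listings of abnormal values. Investigators review and sign the laboratory reports (protocol 5.3.1.1), and a sponsor physician and clinical team review all results (protocol 11.0). Table 8 uses a similar device for high hemoglobin, measuring change from ULN, or from baseline when that is above ULN. Cyclosporine is withdrawn by Week 8, and no renal category is among the adverse events of special interest.

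Much of this stands. A reader might infer that a large creatinine rise would go unreported. The documents do not support that: a value above ULN is still classed as high, tabulated and listed. What is missing is severity. In the shift and incidence tables 1.1 × ULN and 2.9 × ULN look alike, and the table meant to separate them gives neither a PCS flag when the baseline is normal. The hemoglobin comparison also cuts the other way, because that rule states its direction and the creatinine footnote does not.

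Three other stronger readings fail:
- That the footnote picks the less sensitive limit for every subject. It does not for a baseline below LLN, if low counts as abnormal, and the limits coincide at BL = ULN.
- That the missing baseline limit at Grade 4 costs PCS flags. As shown above, it rarely changes PCS status.
- That gamma-GTP, CPK and magnesium are never measured. Protocol 5.3.1.1 allows extra tests when clinically warranted; the supported statement is that they are not in the planned panel.

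**Conclusion.** The point holds for baselines within or above the normal range. There the footnote selects the less sensitive Grade 3 limit, and a more than threefold rise from a normal baseline is not flagged as PCS unless it exceeds 3 × ULN. The gap widens as the baseline falls within the normal range: more than 3.33-fold is needed from 0.9 × ULN and more than 5-fold from 0.6 × ULN. An exactly threefold rise meets neither limit, since both are strict inequalities.

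The result in ULN units needs only that the baseline lies in the normal range. The mg/dL figures rest on an assumed ULN and on 0.6 mg/dL being at or above LLN. The undefined word 'abnormal' matters too: with LLN at 0.5 × ULN and low counted as abnormal, a baseline of 0.49 × ULN is flagged above 3 × 0.49 = 1.47 × ULN, while 0.50 × ULN is flagged only above 3.0 × ULN.

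The consequence is limited to the PCS label. The primary endpoint, the collection of safety data and the other laboratory outputs are unaffected. The three analytes outside the panel are a secondary tidy-up and do not carry the point.

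**What to change.** Replace the creatinine footnote to SAP Table 8 with wording such as: *For PCS Grades 3 and 4, creatinine is graded against both ULN and baseline, and the higher grade is reported. Grades 1 and 2 continue to use ULN if baseline is normal and baseline if it is abnormal.* Add whether abnormal means above ULN only or also below LLN. Grades 1 and 2 should stay as they are, because the Grade 1 baseline limit starts just above 1 × BL and an 'or' there would grade trivial fluctuation.

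In SAP 11.3.1 and Table 8, remove gamma-GTP, CPK and magnesium, or state that only unscheduled results, if any exist, will be graded. That prevents empty rows from being read as an absence of abnormal values.

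The cost is SAP wording and about one programming line, with no change for subjects or sites. The downside is possibly a few more creatinine flags to review. For a baseline below one third of ULN, 3 × BL is less than ULN, so a flag could fall on a value still inside the normal range; the reviewer would see this at once.
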